Target population	 Inclusion criteria Histologically confirmed prostate adenocarcinoma Clinical stage T1c-T3b, N0, M0 Gleason sum 7-10 At least 2 positive cores Prior decision to undergo radical prostatectomy Adult male ≥18 years of age ECOG performance status 0-1, or Karnofsky score ≥ 70% Adequate kidney, liver, and bone marrow function Willingness to sign informed consent and adhere to study requirements Exclusion criteria: Presence of known lymph node involvement or distant metastases Prior radiation, hormones, biologics, or chemotherapy for prostate cancer Prior use of experimental agents for prostate cancer Prior use of experimental agents for prostate cancer History of autoimmune disease requiring systemic immunosuppression History of other malignancy within 3 years Uncontrolled major infectious, cardiovascular, pulmonary, hematologic, or psychiatric illnesses that would make the patient a poor study candidate

IRB#: IRB0010377

Johns Hopkins University

Start date/Initial patients are expected to be entered in November 2016. With an estimatedDurationenrollment rate of 3 patients per month, accrual is expected to last 5-6 months.

The trial was originally designed to evaluate safety and PD endpoint with 16 patients. Based on promising PSA response data prior to prostatectomy, following Enoblituzumab therapy alone, the study will enroll an additional 16 patients for a total size of 32 – amendment 1. All patients will be enrolled utilizing identical inclusion, exclusion, and treatment conditions as the first 16 patients. Expanding the trial to enroll a total of 32 patients will provide statistical power to estimate the clinical benefit of Enoblituzumab in terms of undetectable PSA level (<0.1 ng/mL) 12 months following radical prostatectomy.

Sample size 16 evaluable patients (*i.e.* those that undergo prostatectomy)

16 additional patients in the expansion Amendment 1 will be enrolled for a total sample size of 32 patients.

Rationale Prostate cancer remains the second most common cause of cancer related death in males, killing one in every 36 American men. While advances have been made in early detection and local treatment, few treatments have been able to dramatically alter the course of disease once it progresses to subclinical or clinical metastases. In that setting, androgen deprivation therapy is considered frontline but, while many patients will experience initial tumor regression, their prostate cancer inevitably develops a castrate resistant phenotype. Recent advances in our understanding and ability to manipulate the immune system have resulted in a sea of change in the treatment of aggressive malignancies. One promising approach to metastatic disease involves treatments that use the immune system to target and destroy tumor cells. Because an anti-tumor T cell response has the ability to dynamically evolve, immunotherapy can potentially overcome the genetic diversity of aggressive and advanced cancers. Moreover, because the immune system develops memory, anti-tumor immune responses can be potentially long-lived, and long-lived responses have been reported in patients with melanoma, kidney cancer and bladder cancer. Those recent data mostly involve immune checkpoint blockade using anti-CTLA-4 or anti-PD1/PDL1; but in prostate cancer those therapies have yielded little in the way of objective responses, suggesting the need for alternative immunological approaches.

B7-H3 is part of the B7 superfamily which includes B7-H1(PD-L1) and B7-DC(PD-L2). Although a number of studies document a role for B7-H3 in modulating the immune response, its regulation and mechanism of action are not completely clear, with literature demonstrating both T-cell stimulatory and inhibitory effects. In addition, tumor cell expression of B7-H3 has been associated with an autonomous proliferative and migratory function. Perhaps most relevant, multiple reports (as well as our unpublished data) support a correlation between B7-H3 expression and adverse pathology and clinical outcome in men with prostate cancer. Using a large series of surgical specimens in a cohort of men uncontaminated by hormonal therapy, we found that B7-H3 expression correlates with stage and is associated with biochemical and

clinical progression following treatment. In addition, B7-H3 levels remain high in the presence of androgen deprivation. These studies suggest a potential role for B7-H3 in prostate cancer progression and support its use as therapeutic target in both the hormone naïve and castrate resistant state. Here we propose a neoadjuvant study to determine the anti-tumor, immunological and biological effects of B7-H3 inhibition in men with high-risk prostate cancer.

We aim (1) to investigate whether inhibition of B7-H3 via administration of Enoblituzumab is safe and feasible in the neoadjuvant setting for men with localized intermediate and high-risk prostate cancer; (2) to determine whether Enoblituzumab produces anti-tumor responses by evaluating tumor cell apoptosis in harvested prostate glands; and (3) to determine whether Enoblituzumab is immunogenic in men with localized prostate cancer by evaluating T-cell infiltration in harvested prostate glands. We hypothesize that neoadjuvant Enoblituzumab will be feasible and safe (i.e. will not interfere with subsequent prostatectomy), and will produce measurable tumor cell death and antitumor immune responses.

If this study shows significant tumor cell apoptosis and enhancement of antitumor immunity with Enoblituzumab, and administration of the study drug is feasible and safe, then future studies would aim to use Enoblituzumab in both the adjuvant and the salvage settings. For example, a trial could be designed to assess the efficacy of Enoblituzumab given before and after radical prostatectomy, using PSA recurrence as the primary endpoint. Alternatively, a trial of Enoblituzumab for patients with PSA recurrence could be designed, with metastatic progression as the primary endpoint.

Objectives Primary:

• To confirm the safety and feasibility of Enoblituzumab administered using a standard dose / schedule in the neo-adjuvant setting

In the expansion cohort (Amendment 1):

• PSA₀ Response (Undetectable PSA level <0.1 ng/mL) at 12 months following radical prostatectomy

Secondary:

- To quantify an anti-tumor response to Enoblituzumab
 - TUNEL staining and quantification of tumor cell apoptosis
 - Caspase 3 staining
 - FcGamma Staining (RIIA, RIIB, RIII/RIV) (based on proposed MOA)
 - Pathological response graded according to standard criteria
- To assess the immune response to Enoblituzumab
 - Quantification of CD8 T cell and CD4 T cell infiltration into the tumor / peritumoral area
 - Determine the effect of Enoblituzumab treatment on the CD8 / Treg and CD4 / Treg ratios

- To assess Gleason grade change post neoadjuvant Enoblituzumab treatment, by comparing prostatectomy Gleason sum to pre-treatment biopsy Gleason sum
- To quantify the extent of PD-L1+ cell density in the prostate from harvested prostate glands of treated patients.
- To quantify the NK cell density in tumor tissue from harvested prostate glands of patients
- To quantify tissue androgen concentration (testosterone, dihydrotestosterone) and androgen receptor (AR) protein expression in prostate specimens

[figure not shown]
Exploratory:

- To quantify B7-H3 expression in pre-treatment and post-treatment tumor tissue and correlate with tumor cell apoptosis and time to PSA-recurrence
- To quantify PD-1, LAG3 and TIM3 in pre and post treatment tumor tissue
- Determination of Fc receptor genotype (CD16A, CD32A, CD32B)
- Global expression profiling of pre and post treatment tumor tissue using the immune NanoString immunopanel and Affy microarrays
- TCR Deep Sequencing (Adaptive Biotech) testing hypothesis that successful antitumor response modulates TCR repertoire in peripheral and tumor infiltrating lymphocytes.
- Quantification of antigen-spread using ProtoArray analyses
- Study design This is a single-center, single arm, open-label pilot study evaluating the safety, antitumor effect, and immunogenicity of neoadjuvant Enoblituzumab (MGA271) given prior to radical prostatectomy in men with intermediate and high-risk localized prostate cancer. Patients will be recruited from the outpatient Urology clinic. Eligible patients will receive Enoblituzumab at a dose of 15mg/kg IV given weekly for 6 doses beginning 50 days prior to radical prostatectomy. 14 days after the last dose of Enoblituzumab, prostate glands will be harvested at the time of radical prostatectomy, and prostate tissue will be examined for the secondary endpoints. Follow-up evaluation for adverse events will occur 30 days and 90 days after surgery. Patients will then be followed by their urologists according to standard institutional practices, but will require PSA evaluations every 3 (±1) months during year 1 and every 6 (±2) months during years 2-3.

Study Schema:

IRB#: IRB0010377

Johns Hopkins University

Baseline evaluations:

- Informed consent
- Medical history and physical assessment
- Review of medications
- Vital signs, including height and weight
- Performance status
- Central pathologic review of prostate core biopsies for histological diagnosis and Gleason score
- CT (If allergic to CT scan contrast, obtain MRI with contrast) and/or bone scan, if clinically indicated
- Hematology, coagulation, and chemistry laboratories
- Serum PSA measurement
- Sera for immunoassays

On weekly treatment days (days 1, 8, 15, 22, 29, 36):

- Performance status
- Interval history and focused physical assessment (including vital signs)
- Adverse events/toxicity evaluation
- Hematology and chemistry laboratories
- PBMC collection for TCR repertoire
- Fc Receptor Genotyping on day one
- Blood for PBLs (treatment days 1 and 36 only)
- Administration of Enoblituzumab 15mg/kg IV

IRB#: IRB0010377

Johns Hopkins University

On day 50:

- Medical history and focused physical assessment (including vital signs)
- Review of medications
- Performance status
- Adverse events/toxicity evaluation
- Hematology and chemistry laboratories
- Serum PSA
- Sera for immunoassays
- PBMC collection for TCR repertoire
- Radical prostatectomy
- Pathologic review of surgical specimen according to standard procedures
- Evaluation of harvested prostate gland for tumor cell apoptosis and CD8⁺ T cell infiltration and other secondary endpoints

Post-operative day 30 and day 90:

- Performance status
- Adverse events/toxicity evaluation
- Hematology and chemistry laboratories
- PSA every 3 months (post-op year 1), then every 6 months (post-op years 2-3)
- Sera for immunoassays
- PBMC collection for TCR repertoire
- Blood for PBLs (Post-op day 30 only)

Criteria for Primary endpoint:

evaluation

• Frequency, type, and severity of adverse events

In expansion (Amendment 1):

• PSA₀ Response (Undetectable PSA level <0.1 ng/mL) at 12 months following radical prostatectomy

Secondary endpoints:

- Mean levels of apoptotic markers (TUNEL staining, caspase 3 staining, and FcGamma staining) and proliferation markers (Ki-67) in prostate tumor specimens of treated patients
- Mean CD8+ T cell density in tumor tissue from harvested prostate glands of patients
- To quantify the extent of PD-L1+ cell density in the prostate from harvested prostate glands of treated patients
- Mean T_{reg} density in tumor tissue from harvested prostate glands of patients
- Mean CD8+/ T_{reg} and CD4+/ T_{reg} ratios in tumor tissue from harvested prostate glands of patients
- Mean CD4+ T cell density in tumor tissue from harvested prostate glands of patients
- Mean NK cell density in tumor tissue from harvested prostate glands of patients

- Proportion of treated patients with detectable Enoblituzumab in prostate tumor specimens(fresh frozen section)
- Proportion of pathological complete responses (pCR) in each treatment group
- Proportion of patients achieving a PSA response rate (PSA <0.1 ng/mL) at 3 months after prostatectomy
- Median time-to-PSA-recurrence (PSA ≥0.2 ng/mL) after radical prostatectomy
- Median PSA decrease prior to radical prostatectomy
- To assess Gleason grade change post neoadjuvant Enoblituzumab treatment, by comparing prostatectomy Gleason sum to pre-treatment biopsy Gleason sum

Statistical Our primary objective(s) is to characterize safety, tolerability, and feasibility of treatment of men with Enoblituzumab in the neoadjyuant setting as well as obtain an methods estimate of PSA₀ response rate 12 months following radical prostatectomy. The trial will monitor toxicity and safety, as well as feasibility with respect to its impact on subsequent surgery. The secondary objective will be to evaluate an anti-tumor effect consistent with the agent's proposed mechanism of action (MOA), antibody-dependent cellular cytotoxicity (ADCC). Tumor cell death will be quantified by Caspase staining, and post-treatment apoptotic index compared with that from the pre-treatment biopsy. Sample size is driven by detecting a pharmacodynamic effect of the agent based on the key secondary endpoint of tumor cell death as well as in the expansion cohort to obtain an estimate of PSA_0 response. A biologically meaningful treatment effect will be deemed to be one where the tumor cell apoptosis is two-fold higher after Enoblituzumab therapy. Previous study showed that baseline apoptosis, measured by Caspase staining, is 0.06 +/- 0.08 (Mean +/-SD) for Gleason 4 and 0.2 ± 0.2 for Gleason 3 (Kim et al 2016). Based on this data, we assume that the coefficient of variation of tumor cell death measure is 1.2 and the correlations between the measures pre- and post-treatment is moderate at 0.4, 16 subjects will provide 88% power to detect a 2-fold increase in apoptotic tumor cells after the treatment compared to baseline, using a one-sided paired t-test with significance level 0.05. Other endpoints will be exploratory in nature, and quantified using descriptive statistics.

For the expansion cohort (amendment 1):

Our primary efficacy endpoint with 32 patients will be to estimate the clinical benefit of neoadjuvant Enoblituzumab in terms of undetectable PSA level (<0.1 ng/mL) at 12 months following radical prostatectomy. There are currently no approved neoadjuvant treatments for high risk localized prostate cancer and we believe future larger neoadjuvant trials can be better designed in high risk patients if we can estimate the benefit as per the below table showing the 90% confidence interval.

Johns Hopkins University

Observed N with undetectable PSA	Observed rate	90% CI
0	0	0% - 7.8%
1	3.1%	0.7% - 12.9%
2	6.2%	2.1% - 17.2%
3	9.4%	3.8% - 21.3%

Safety analysis Frequency, types, and grades of adverse events in each treatment group will be measured using the NCI Common Toxicity Criteria version 4.0, and will be summarized using descriptive statistics. Formal safety assessments will be performed from the time of first administration of Enoblituzumab until the 90th postoperative day.

Johns Hopkins University

TABLE OF CONTENTS

1.	OBJE	OBJECTIVES		
	1.1	Primary Objectives	16	
	1.2	Secondary Objectives	16	
	1.3	Exploratory Objectives	16	
2.	BAC	KGROUND AND RATIONALE	18	
	2.1	Disease Background	18	
	2.2	Treatment Background	19	
	2.3	Rationale	23	
3.	PAT	IENT SELECTION	25	
	3.1	Target Population	25	
	3.2	Inclusion Criteria	25	
	3.3	Exclusion Criteria	26	
	3.4	Inclusion of Minorities		
	3.5	Prohibited Concomitant Medications	27	
4.	REG	ISTRATION AND ENROLLMENT PLAN	27	
	4.1	Registration Procedure	27	
	4.2	Expected Enrollment	28	
	4.3	Study Centers	28	
	4.4	Recruitment	28	
5.	STU	DY PLAN	28	
	5.1	Overview and Schema	28	
	5.2	Screening/Pretreatment Evaluation	32	
	5.3	Treatment Visits		
	5.4	Radical Prostatectomy		
	5.5	Follow-Up Evaluations	33	
	5.6	Duration of Therapy	34	
6.	STU	DY TREATMENT	34	
	6.1	Description of Study Drug and Supplies		
	6.2	Drug Preparation	35	
7.	ADV	ERSE EVENTS AND REPORTING REQUIREMENTS	42	
	7.1	Recording and Grading	42	
	7.2	Unexpected Adverse Events	44	
	7.3	Serious Adverse Events and Serious Adverse Drug Reactions	44	
	7.4	Perioperative Adverse Events		
	7.5	Reporting Adverse Events	46	
	7.6	Pregnancy	48	
8.	OUT	COME ASSESSMENT	48	
	8.1	Radical Prostatectomy Specimen	48	
	8.2	Primary Endpoint	49	
	8.3	Secondary Endpoints	49	
9.	REG	ULATORY AND REPORTING REQUIREMENTS	53	
	9.1	Regulatory Responsibilities		
	9.2	Data Management	54	
	9.3	Study Monitoring and Quality Assurance	54	

Johns Hopkins University

10.	STATISTICAL CONSIDERATIONS	

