d: Chemistry laboratories include sodium, potassium, chloride, bicarbonate, urea nitrogen, creatinine, glucose, calcium, albumin, total protein, bilirubin, alanine aminotransferase (ALT), aspartate aminotransferase (AST), alkaline phosphatase, amylase, and lipase.

e: Serum PSA should be obtained pre-treatment (at least 30 days from biopsy) and on the day of surgery, and every 3 months (±1 mo) for post-op year one then every 6 months (±2 mo) for post-op years two and three.

f: Harvested prostate gland to be evaluated for tumor apoptosis, CD8⁺ T cell infiltration, as well as other secondary and exploratory endpoints.

g: Archival prostate core biopsies to be centrally reviewed at baseline prior to study entry; radical prostatectomy specimens to be processed at Johns Hopkins according to standard procedures. Archival tissue for B7-H3 IHC testing to be sent to MacroGenics.

h: The post-operative evaluations (30 and 90 days after prostatectomy) may take place over the telephone or in person, but patients are required to have hematology and chemistry labs collected at this time-point for safety purposes.
i: In addition, PSA should be measured every 3 months (±1 month) in the first year after prostatectomy, and every 6

months (±2 months) in the second and third years after prostatectomy.

- Fc Receptor Genotyping and TCR Repertoire is collected prior to treatment in one 8.5 mL PaxGene DNA collection j:
- tube. TCR Repertoire is collected on the day of surgery, and 30 and 90 days post-op. PBLs should be collected on treatment day 1 (pre-treatment), treatment day 36 (post-treatment), and follow-up day k: 30 (see Appendix F)
- See Appendix F for specimen collection instructions for Sera for immunoassays.

IRB#: IRB0010377

Johns Hopkins University

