5.5 Follow-Up Evaluations

Follow-up visit scheduled for 30 days and 90 days after radical prostatectomy may occur in the outpatient clinic. Required evaluations during this follow-up visits are listed below. Patients should then continue to be followed by their treating urologist according to standard institutional practices.

- performance status
- review of medication list
- review of toxicity/adverse events
- hematological laboratories and serum chemistry profile
- Serum PSA at post-operative day 90
- Sera for immunoassays
- PBMC collection for TCR Repertoire
- Whole blood for PBLs (post-op day 30 only)

Patients withdrawing from the study early because of adverse events should be followed until the adverse event has either resolved or stabilized. Reasons for premature withdrawal should be determined and documented.

In addition, patients will be required to have a structured assessment of post-operative PSA measurements for 3 years. In the first year after prostatectomy, PSA will be measured every 3 months (±1 mo). In the second and third years after prostatectomy, PSA will be measured every 6 months (±2 mo). These PSA measurements may be obtained outside of Johns Hopkins, but the results need to be made available to the study team.

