8.3.17 PSA response rates

This will be defined as the proportion of patients who achieve an undetectable PSA (<0.1 ng/mL) by 3 months after prostatectomy. The endpoint will be expressed as the proportion of men achieving a PSA response.

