8.3.18 Time to PSA recurrence

This will be defined as the interval from the time of prostatectomy to the time when the serum PSA is ≥ 0.2 ng/mL. PSA will be measured approximately 1 month after prostatectomy, and every 3 (±1) months during the first post-operative year and every 6 (±2) months during the second and third post-operative years. For subjects who have not yet demonstrated PSA relapse at the time of censoring, patients will be censored at the date of

the last assessment that shows a lack of PSA recurrence. This outcome will be expressed as a median and will be determined using the Kaplan-Meier method.

8.3.19 In expansion cohort (Amendment 1): assessment of Gleason grade change (prostatectomy Gleason sum vs. core biopsy Gleason sum) post neoadjuvant Enoblituzumab treatment

This will be defined by comparing highest Gleason grade from pre-treatment biopsy versus highest Gleason grade from post-treatment prostatectomy. This endpoint will be expressed as the proportion of men achieving a Gleason score change.

8.3.20 Global expression profiling of pre and post treatment tumor tissue using single cell RNA sequencing, the immune NanoString immunopanel and/or microarrays

Expression profiling will be conducted as per established protocols for single cell RNA seq, Nanostring, and microarray

8.3.21 IHC analyses of CD137, CD16 and/or CD107A across potential immune infiltrate following Enoblituzumab

CD137, CD107A, and CD16 expression in prostate tumor specimens will be assessed by IHC in the prostatectomy surgical specimens (post-treatment). This endpoint will be expressed as the mean staining percentage of each of these in in tumor tissue.

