- **Regulatory T cell (T_{reg}) density**. The methods for analyzing T_{reg} infiltration will be similar to those described for CD8⁺ T cell infiltration. Descriptive statistics and graphical summaries will be provided. In addition, the CD8⁺/T_{reg} ratio and the CD4⁺/T_{reg} ratio will be computed, and reported using descriptive statistics.
- **CD4**⁺ **T cell density.** The methods for quantifying and analyzing CD4⁺ T cell infiltration will be similar to those described for CD8⁺ T cell infiltration. Descriptive statistics and graphical summaries will be provided.
- **Mean NK cell density**. The methods for quantifying and analyzing NK cell infiltration will be similar to those described for CD8+ T cell infiltration. Descriptive statistics and graphical summaries will be provided.
- **Tissue androgen concentrations**. Intraprostatic androgen concentrations (*i.e.* testosterone and dihydrotestosterone) will be summarized descriptively.
- **Enoblituzumab (MGA271) drug distribution**. Intraprostatic Enoblituzumab staining concentrations will be summarized descriptively.
- Androgen receptor (AR) quantification. Androgen receptor (AR) staining concentrations will be summarized descriptively.
- **Pathological complete responses (pCR)**. This will be defined as an absence of tumor identification on standard histological analysis of the resected prostate specimens.
- **PSA response rates**. This will be defined as an undetectable PSA (<0.1 ng/mL) at 3 months after prostatectomy. The proportion of patients achieving a PSA response will be reported. .
- **Time to PSA recurrence.** This will be defined as the interval from prostatectomy to the time when the serum PSA is ≥0.2 ng/mL. For subjects who have not yet demonstrated PSA recurrence at the time of censoring, patients will be censored at the date of the last

assessment that shows a lack of PSA recurrence. The median time to PSA recurrence after prostatectomy (*i.e.*, the median PSA-recurrence-free survival) will be estimated with 95% confidence intervals using Kaplan-Meier survival analysis.

• **Gleason grade change** post neoadjuvant Enoblituzumab treatment from pre-treatment biopsy. This will be calculated utilizing the highest Gleason grade from the pre-treatment biopsy and the post-treatment prostatectomy.

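### PSA recurrence is triggered by one unconfirmed PSA of 0.2 ng/mL or more, and the month-1 draw that can trigger it is not scheduled consistently

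*Combined protocol and SAP*

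**What the plan says.** The endpoint appears in the synopsis (Criteria for evaluation) as "Median time-to-PSA-recurrence (PSA ≥0.2 ng/mL) after radical prostatectomy". That line gives only the threshold. The operative definitions are in Section 8.3.18, "This will be defined as the interval from the time of prostatectomy to the time when the serum PSA is ≥ 0.2 ng/mL", and Section 10.2.2, "This will be defined as the interval from prostatectomy to the time when the serum PSA is ≥0.2 ng/mL". Neither section, nor any other text, asks for a second value, a prior undetectable value or an earliest eligible date. There is also no rule for a PSA that never becomes undetectable. Men without an event are censored at their last assessment showing no recurrence.

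The schedule is described in different ways:

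- Section 8.3.18: "PSA will be measured approximately 1 month after prostatectomy, and every 3 (±1) months during the first post-operative year".
- Section 5.5, in the list for the day-30 and day-90 visits: "Serum PSA at post-operative day 90". No day-30 PSA is listed.
- Table 1, footnote e: "every 3 months (±1 mo) for post-op year one then every 6 months (±2 mo) for post-op years two and three". No 1-month draw is named.
- Table 1 itself has one column for days 30 and 90, with a PSA mark that points to footnote e.

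Two other endpoints use the same PSA series. Section 8.3.17 counts men "who achieve an undetectable PSA (<0.1 ng/mL) by 3 months after prostatectomy", while Section 10.2.2 says at 3 months. The expansion's primary efficacy endpoint (Sections 8.2.2 and 10.2.1.1) is PSA below 0.1 ng/mL at 12 months. Neither response excludes a man with an earlier value of 0.2 or more.

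**The concern.** In a Kaplan-Meier analysis an event cannot be undone. If one reading suffices, a value that is not sustained removes the man from the risk set for good and pulls the curve down. The plan would then report him as recurred even though all his later values are below 0.1.

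The month-1 draw adds uneven ascertainment. If some men have it and others do not, the chance of an early event depends on who was tested. Section 5.5 also lets post-operative PSAs be obtained outside the institution, which is a further practical reason not to rely on one reading.

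Two uses are affected: the secondary time-to-recurrence estimate, and the exploratory correlation of B7-H3 expression with time to PSA recurrence (Section 1.3). Section 2.3.1 names PSA recurrence as a possible primary endpoint for a later trial, so the estimate may be carried forward.

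**Working it through.** The plan states no figure that depends on this definition, so there is none to reproduce. The check applies the definitions to example PSA sequences and then sizes the effect under a labelled assumption.

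**Step 1: apply the rules as written (PSA in ng/mL).**

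| Man | PSA sequence | Recurrence (8.3.18, 10.2.2) | 3-month response | 12-month PSA0 response |
|---|---|---|---|---|
| A | 0.3 at month 1; below 0.1 from month 3 to month 12 | Event at month 1 | Yes | Yes |
| B | Below 0.1 to month 6; 0.2 at month 9; below 0.1 at month 12 | Event at month 9 | Yes | Yes |
| A, month-1 PSA not drawn | Below 0.1 from month 3 to month 12 | No event | Yes | Yes |

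The first and third rows are the same man. Only the presence of the month-1 draw differs.

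**Step 2: count the scheduled draws.** Footnote e gives months 3, 6, 9 and 12, then 18 and 24, then 30 and 36: 4 + 2 + 2 = 8. Section 8.3.18 would add month 1 as a ninth.

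**Step 3: illustration, by assumption only.** Let q be the chance, per draw and independent between draws, that a non-recurring man shows an isolated value of 0.2 or more. The documents give no value for q. The chance of at least one false event over 8 draws is 1 − (1 − q)^8:

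- q = 0.5%: 1 − 0.995^8 = 3.9%
- q = 1%: 1 − 0.99^8 = 7.7%
- q = 2%: 1 − 0.98^8 = 14.9%

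If the next draw must also be 0.2 or more, there are 7 consecutive pairs, and the chance is at most 7q²:

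- q = 0.5%: 7 × 0.000025 = 0.02%
- q = 1%: 7 × 0.0001 = 0.07%
- q = 2%: 7 × 0.0004 = 0.28%

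**Step 4: effect on the curve.** With 32 men and no earlier censoring, each month-1 event lowers the estimate by 1/32 = 3.1 percentage points. Moving the median to month 1 would take 16 such events (16/32 = 50%).

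**Step 5: apply the confirmation rule.** Man A's month-3 value and man B's month-12 value are both below 0.2, so neither is an event. A man at 0.3 at months 1 and 3 is an event dated month 1. Without the month-1 draw, and still at 0.3 at month 6, he is dated month 3. Confirmation therefore removes the false event but not the dating difference, so the schedule must be reconciled as well.

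**The case against.** The strongest reply is that little rests on this endpoint. It is one secondary endpoint in a single-arm study, the synopsis treats the remaining endpoints as exploratory and descriptive, and no sample size, alpha or stopping rule uses it. A few false events need not move the median. All of that stands and limits the weight of the point.

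It can also be said that time to first PSA of 0.2 or more and PSA below 0.1 at a landmark are different endpoints with different thresholds, so one man may legitimately meet both. That is correct in general. A man with confirmed recurrence who is treated and is below 0.1 at month 12 would still be counted in both after the change. The defect is narrower: an isolated value that is not sustained should not count as a recurrence.

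Two stronger readings are tempting. First, a reader might infer from the 3-month response endpoint that men are not expected to have cleared PSA at month 1, so that month-1 events would be systematically premature. The documents give no clearance time, half-life or baseline PSA distribution, and judging response by or at 3 months does not show that clearance is incomplete at 1 month. Second, a reader might combine an assumed error rate with the 30–50% recurrence in Section 2.1 to state what share of all events would be false. That range is local or distant recurrence after definitive local therapy in general, with no time frame. It is not PSA recurrence within 3 years of prostatectomy and cannot serve as the denominator.

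**Conclusion.** The point holds in this form: the definition makes one unconfirmed PSA of 0.2 or more a permanent event, and it draws on a month-1 PSA that the follow-up list and calendar footnote do not name. Followed literally, it counts as recurred a man whose later values are all below 0.1 and who is a 12-month PSA0 responder. This follows from the text alone.

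Its size cannot be derived from the documents. The 3.9%, 7.7% and 14.9% figures rest wholly on the assumed per-draw rate and on independence; they show sensitivity and are not an estimate for this trial. The consequence is confined to a descriptive secondary endpoint and the exploratory B7-H3 correlation. It is worth correcting because the definition gives a wrong classification and the correction is small.

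**What to change.** In Sections 8.3.18 and 10.2.2:

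1. Define recurrence as a PSA of 0.2 ng/mL or more that is also 0.2 or more at the next scheduled PSA, and date the event at the first of the two values.
2. If treatment for recurrence is known to have started before a confirming value, count the first value as the event.
3. Apply the same rule to any month-1 value: one that then falls below 0.2 is not an event, and a PSA that stays at 0.2 or more is.
4. Reconcile the month-1 PSA in Section 8.3.18 with Section 5.5 and Table 1 footnote e.
5. Report the single-value definition, including an unconfirmed rise at the last visit, as a sensitivity analysis.

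The cost is mainly wording, because confirmation uses PSA values already scheduled. The downsides are that a rise at the last visit stays unconfirmed in the main analysis, and that in years 2–3 confirmation comes about 6 months later (±2 months). Item 2 can use only what is known: Section 6.5 records concomitant medication only to the post-treatment follow-up visit, and later treatment is not a structured data item. That is why it is worded as known treatment and adds no new data collection.
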